9.1 Study Design

Phase II single arm study evaluating the potential efficacy in improving the PSA-CR with combined enzalutamide and leuprolide therapy in patients with high-risk prostate cancer or pelvic node involvement undergoing definitive radiation therapy. Also the safety and feasibility of combined enzalutamide and leuprolide therapy in patients undergoing radiation therapy will be determined.

9.2 Determination of Sample Size and Accrual Rate

9.2.1 Sample Size and Power Estimate

Sample size is determined based on the primary objective of the PSA-CR. This is a single arm study with the primary endpoint evaluating the proportion of patients experiencing a PSA-CR. From historical controls (RTOG 9413 and MSKCC as mentioned in background information), we expect 70% of patients to experience a PSA-CR. With addition of enzalutamide, at least 85% of patients are expected to attain a PSA-CR. With 53 patients (10% dropout rate), we would have 80% power to detect thus improvement at significance level of 0.05 based on directional binomial test.

As we expect the combined enzalutamide and leuprolide regimen does not significantly increase grade 3 or greater acute or late toxicity for treatment of intermediate- to high-risk prostate cancer and the usual rate of 3 or greater toxicity is approximately 12%. If the true grade 3 or greater acute or late toxicity rate is 12%, with 47 patients we will have 80% confidence in the toxicity rate estimate with precision of 4.7% (i.e. a confidence interval width of 9.4%).

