2.4 Endpoints

2.4.1 Primary Endpoint

1. The primary endpoint of the study is to determine the rate of acute toxicity (≤ 90 days within the completion of radiotherapy) and late toxicity (≥ 91 days within the completion of radiotherapy). Adverse events will be defined according to CTCAE v. 4.0 criteria. Patients will be monitored at least weekly during treatment and every 3-6 months up to 24 months and at 36 months after radiation therapy.
2. A PSA measurement will be obtained at 120-127 days after initiation of androgen deprivation therapy. The proportion of patients achieving a PSA-CR (PSA nadir ≤ 0.3) at 120-127 days will be determined. The historical proportion of patients (0.7) attaining a PSA-CR from RTOG 9413 will be utilized for comparison.

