9.2.2 Accrual estimates

A total of 53 patients with very high-risk prostate cancer or with pelvic nodal involvement without distant metastases will be enrolled. Study accrual is anticipated to be approximately 3 patients per month, with a goal complete accrual by 24 months.

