9.4.2 Primary Analysis (or Analysis of Primary Endpoints)

Point estimates and 95% confidence intervals of PSA-CR will be obtained. The PSA-CR will be compared with the historical rate by binomial test.

Toxicity will be assessed by CTCAE v4.0. Point estimation and its 95% confidence interval will be calculated for the rate of acute Grade 3 or greater toxicity within 24 months of completing treatment with radiotherapy. Furthermore, one sample proportion test will be used to test hypothesis that the addition of enzalutamide to leuprolide and radiation therapy does not significantly increase acute or late toxicity.

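### The 80% power stated for PSA-CR is about 75% under an exact one-sided binomial test once 10% dropout is allowed for (73% at 47 evaluable, 71% at 48)

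*Combined protocol and SAP*

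**What the plan says.** Section 9.2.1 takes the sample size from the PSA-CR objective. The null rate comes from historical controls ("we expect 70% of patients to experience a PSA-CR"), and Section 2.4.1 uses the same benchmark ("The historical proportion of patients (0.7) attaining a PSA-CR from RTOG 9413 will be utilized for comparison"). The alternative is that "at least 85% of patients are expected to attain a PSA-CR". The power statement is "With 53 patients (10% dropout rate), we would have 80% power to detect thus improvement at significance level of 0.05", and the test is described as "at significance level of 0.05 based on directional binomial test".

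Section 9.2.2 shows that 53 is the number before dropout: "A total of 53 patients with very high-risk prostate cancer or with pelvic nodal involvement without distant metastases will be enrolled". The toxicity paragraph of 9.2.1 then works with 47 ("with 47 patients we will have 80% confidence in the toxicity rate estimate"), which fits 53 less about 10%.

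For the analysis, Section 9.4.2 says "The PSA-CR will be compared with the historical rate by binomial test". Neither section says whether the test is exact or approximate, and no critical number of responders is given.

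**The concern.** A binomial test is usually read as the exact test. Responder counts are whole numbers, so its true alpha at a given sample size is often well below 0.05, and its power is then below what a smooth approximation suggests. If the sample size came from an approximation and the analysis uses the exact test, the stated power is not the power of the planned analysis.

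Two things are at stake. The 80% is the figure that sizes the trial, so an overstatement understates the risk of missing the improvement the trial was built to detect. And with no form of test and no cut-off fixed in advance, a borderline count could be called a success or a failure depending on a choice made after the data are seen.

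**Working it through.** **Inputs.** Null rate p0 = 0.70 (Sections 2.4.1 and 9.2.1); alternative p1 = 0.85, one-sided alpha 0.05 and 10% dropout (9.2.1); 53 enrolled (9.2.2). Evaluable: 53 × 0.9 = 47.7, so 47 or 48; the plan itself uses 47.

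**Reproducing the plan's figure.** Arcsine approximation:

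- h = 2·arcsin(√0.85) − 2·arcsin(√0.70) = 2.3462 − 1.9823 = 0.3639.
- n = ((1.645 + 0.842) / 0.3639)² = 46.7, so 47.
- Power at 47 = Φ(0.3639 × √47 − 1.645) = 80.2%.
- 47 / 0.9 = 52.2, so 53 enrolled.

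The 47, the 53 and the 80% all reproduce. The usual one-sample normal approximation comes slightly lower: 77.9% at 47 and 78.8% at 48.

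**Exact test.** For each evaluable n, take the smallest cut-off c with P(X ≥ c | n, 0.70) ≤ 0.05. Power is then P(X ≥ c | n, 0.85).

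| Evaluable n | Cut-off c | True alpha | Power |
|---|---|---|---|
| 44 | 37 | 0.026 | 66.3% |
| 45 | 37 | 0.047 | 77.5% |
| 46 | 38 | 0.039 | 75.4% |
| 47 | 39 | 0.033 | 73.3% |
| 48 | 40 | 0.027 | 71.2% |
| 49 | 40 | 0.048 | 80.9% |
| 50 | 41 | 0.040 | 79.1% |
| 51 | 42 | 0.034 | 77.3% |
| 52 | 43 | 0.028 | 75.4% |
| 53 | 43 | 0.048 | 83.8% |

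Power is saw-toothed. In this range it reaches 80% only at 49 and 53.

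**Can a lower cut-off recover the power?** Not within the stated alpha. At n = 47, 38 responders has true alpha 0.067; at n = 48, 39 has 0.057.

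**Averaging over dropout.** With the evaluable count distributed as Binomial(53, 0.9), mean exact power is 75.4%. The probability that the count lands where exact power is under 80% is 0.83.

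**Score z-test.** z = (x/n − 0.70) / √(0.21/n), compared with 1.645.

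- n = 47: 38 responders gives z = 1.62 and 39 gives 1.94. The cut-off is 39, as in the exact test, so power is again 73.3%.
- n = 48: 39 responders gives z = 1.70. The cut-off is 39, with power 82.6% but true alpha 0.057. The exact test requires 40.

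**Effect size.** With a cut-off of 39 out of 47, 80% power requires a true PSA-CR rate of 86.1% rather than 85%.

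**The case against.** The strongest reply is that nothing has been miscalculated. The arcsine method returns all three of the plan's numbers, and the word exact appears nowhere. That is right as far as it goes: the fault is best described as a mismatch between the sizing approximation and the test named for analysis. That the arcsine formula was the one used is an inference.

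The size of the gap also depends on the form of test. Averaged over the same dropout, the score z-test gives 78.3% and a mid-p binomial test 80.3%. But these variants pass 80% at 47 or 48 only by exceeding the stated alpha: mid-p at 47 uses cut-off 38 (true alpha 0.067), and both use 39 at 48 (0.057). At 47, the plan's own number, the z-test does no better than the exact test.

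Next, 47 and 48 sit near a low point of the saw-tooth, so 7 to 9 points overstates the typical loss. This stands, and the 5-point average is the fairer summary.

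Finally, the average assumes that dropouts leave the denominator. Section 9.4.1 says all patients are analysed and gives no rule for a missing day 120–127 PSA. If all 53 have a PSA, exact power is 83.8%. If dropouts count as non-responders, the response rate is 0.85 × 0.9 = 0.765 and power is about 27%. Excluding dropouts is the reading that fits the 10% allowance and the use of 47, but the plan does not state it.

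**Conclusion.** The concern holds. For the exact form of the one-sided binomial test named in Sections 9.2.1 and 9.4.2, power to detect 85% against 70% averages 75.4% after 10% dropout, about 5 points below the stated 80%; it is 73.3% at 47 evaluable and 71.2% at 48. The chance of missing a true 85% rate is about 25% on average (27% at 47, 29% at 48), not 20%.

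This rests on three assumptions: the test is exact, dropout is independent between patients at 10%, and dropouts are left out of the denominator. The first is a reading of the plan, but at 47 or 48 evaluable no fixed cut-off gives both 80% power and a true alpha of at most 0.05. The design remains usable. The stated power and the missing success criterion should be corrected before analysis.

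**What to change.** Restate the power in Section 9.2.1, for example:

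> With 47 evaluable patients, success is at least 39 PSA-CRs (exact one-sided alpha 0.033), with 73% power against a true rate of 85%. With all 53 evaluable, success is at least 43 (alpha 0.048), with 84% power. For any other evaluable count, the cut-off is the smallest number of PSA-CRs with exact one-sided p ≤ 0.05.

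In Section 9.4.2, name the analysis as the exact one-sided binomial test against 0.70. It would help to say there who counts as evaluable when the day 120–127 PSA is missing, since the cut-off depends on that count.

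The change is to wording only and needs no extra patients. Its one downside is a less favourable stated power. If 80% is to be kept under the exact test, average power after 10% dropout first reaches it at 59 enrolled (80.1%), six more than planned; that is an option, not a requirement of this fix.

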7.1 Definitions

Evaluable for toxicity

All patients will be evaluable for toxicity from the time of their first treatment with the study drug until 24 months after last dose of enzalutamide treatment.

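### The toxicity precision in section 9.2.1 is overstated: with 47 patients, ±4.7 points is about 68% confidence, and a two-sided 80% interval is about 12.1 points wide, not 9.4

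*Combined protocol and SAP*

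**What the plan says.** Section 9.2.1 of the combined protocol and SAP first sets the trial's size: "Sample size is determined based on the primary objective of the PSA-CR". It arrives at 53 patients, allowing for 10% dropout. It then describes what the trial can say about toxicity. The premise is "If the true grade 3 or greater acute or late toxicity rate is 12" percent. The claim is that "with 47 patients we will have 80% confidence in the toxicity rate estimate with precision of 4.7" percent, which the text explains in brackets as "i.e. a confidence interval width of 9.4" percent. No interval method is named and no derivation is shown.

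Three other sections bear on this:

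- Section 2.4.1 lists toxicity first among the primary endpoints: "The primary endpoint of the study is to determine the rate of acute toxicity", followed by late toxicity.
- Section 9.4.2 plans the analysis at a different confidence level: "Point estimation and its 95% confidence interval will be calculated for the rate of acute Grade 3 or greater toxicity".
- Section 7.1 sets the toxicity population: "All patients will be evaluable for toxicity from the time of their first treatment with the study drug". The number available for toxicity could therefore be as high as 53.

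**The concern.** The sentence supplies every input needed to check it: the rate, the number of patients, the confidence level, the half-width and the full width. For a 12% rate in 47 patients, one standard error is already 4.7 points, and an 80% two-sided interval must extend about 1.28 standard errors each side. The stated precision therefore looks too small for the stated confidence.

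At stake is how well the trial can pin down a primary endpoint. This sentence is the plan's only quantitative statement of what the sample size delivers for toxicity. A reader who accepts it expects a tighter interval than the design can give. The gap widens at the 95% level of section 9.4.2, for which section 9.2.1 gives no figure.

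**Working it through.** **Inputs.** From section 9.2.1: true rate p = 0.12, n = 47, confidence 80%, half-width 4.7 points, width 9.4 points, and total enrolment 53. From section 9.4.2: a 95% interval in the analysis. Sidedness is not stated, but a full interval width is, so the interval is taken as two-sided.

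**Step 1: where 4.7 appears.** The standard error is √(p(1 − p)/n) = √(0.12 × 0.88 / 47) = √(0.1056 / 47) = 0.0474, or 4.74 points. The stated 4.7 matches one standard error numerically. The plan does not say whether it was obtained that way.

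**Step 2: the confidence that ±4.7 points carries.** By the normal approximation, 2Φ(0.047 / 0.0474) − 1 = 0.679, about 68%. As an exact binomial check, the observed rate lies within 4.7 points of 12% when there are 4 to 7 events among 47. That has probability 0.635. The exact figure is sensitive to n because the data are discrete: the same check gives 0.728 at n = 48 and 0.714 at n = 53. None of these reaches 80%.

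**Step 3: the 80% interval.** The half-width is z(0.90) × SE = 1.2816 × 0.0474 = 0.0607, or 6.1 points. The full width is 0.1215, about 12.1 points. Against the stated width, 0.1215 / 0.094 = 1.29.

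**Step 4: other methods and the larger n.** The table gives expected widths of two-sided 80% intervals in percentage points, averaged over the binomial distribution with p = 0.12.

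| Method | n = 47 | n = 53 |
|---|---|---|
| Wald | 11.8 | 11.2 |
| Wilson | 11.9 | 11.3 |
| Agresti-Coull | 12.2 | 11.5 |
| Jeffreys | 11.8 | 11.2 |
| Clopper-Pearson | 13.9 | 13.0 |

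None is near 9.4. The expected Wald width (11.8) is slightly below the 12.1 of Step 3 because Step 3 fixes the estimate at exactly 12%, while the table averages over the possible estimates.

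With all 53 patients, SE = √(0.1056 / 53) = 0.0446. The 80% half-width is then 5.7 points and the width 11.4.

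**Step 5: patients needed for ±4.7 points at 80%.** n = 1.2816² × 0.1056 / 0.047² = 78.5, so 79.

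**Step 6: the 95% level.** By the normal approximation, at n = 47 the half-width is 1.96 × 0.0474 = 0.0929, or 9.3 points (width 18.6). At n = 53 it is 8.7 points (width 17.5). The expected width of an exact Clopper-Pearson 95% interval is about 20.0 points at n = 47 and 18.8 at n = 53.

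**The case against.** The strongest rescue is a one-sided reading, since the plan does not state sidedness. With 47 patients and a true rate of 12%, the probability of 7 or fewer events is 80.3%. There is thus about an 80% chance that the observed rate exceeds 12% by no more than 4.7 points. Two things count against this reading:

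- Any margin from about 2.9 points (7/47 − 0.12) up to about 5.0 points (8/47 − 0.12) gives the same probability, so the calculation does not single out 4.7.
- The plan gives a full interval width of 9.4, which is a two-sided statement that this reading does not deliver.

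Other one-sided variants do no better. The one-sided 80% half-width at n = 47 is 0.8416 × 0.0474 = 3.99 points, or 5.05 with a continuity correction. A one-sided multiplier with continuity correction does return 4.70 at n = 53. But the text says 47 patients, and a two-sided interval built with that multiplier is nominally 60%.

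The second objection is about importance, and it largely stands. The sample size comes from PSA-CR, the termination rules in sections 3.4 and 9.3 use a 12% threshold and not an interval, and section 9.4.2 fixes the reported interval separately. Correcting the sentence changes no estimate, test or enrolment decision. It remains a wrong figure for a primary endpoint.

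It is also fair to say that planning precision need not be quoted at the analysis level. The missing 95% figure is a gap in usefulness, not an arithmetic error.

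**Conclusion.** The stated precision is wrong as written. At a 12% rate with 47 patients, ±4.7 points carries about 68% two-sided confidence, not 80%. The two-sided 80% half-width is about 6.1 points, and the width about 12.1 against the stated 9.4. With all 53 patients the 80% width is still 11.4.

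The headline figures assume a two-sided interval and the normal approximation. The other four interval methods checked also give widths well above 9.4, and the exact method gives the widest.

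The consequence is limited to an overstated precision for a primary endpoint. The sample size and the decision rules are unaffected. This should be fixed.

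One limit applies to the 95% figures. Section 9.2.1 speaks of acute or late toxicity, while the interval in section 9.4.2 is worded for acute toxicity. The 95% figures here describe the section 9.2.1 rate at that confidence level, not that specific interval.

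**What to change.** Replace the precision statement in section 9.2.1 with one along these lines:

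> Assuming a true rate of 12% for acute or late toxicity of grade 3 or higher, 47 patients give a normal-approximation half-width of about 6.1 percentage points for a two-sided 80% confidence interval (width about 12.1). For a 95% interval, the confidence level used in section 9.4.2, the half-width is about 9.3 points (width about 18.6). With all 53 patients the half-widths are 5.7 and 8.7 points. An exact (Clopper-Pearson) 95% interval would be somewhat wider, with an expected width of about 20 points at 47 patients and 19 at 53.

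If a shorter text is preferred, one corrected half-width and width, with the confidence level and n stated, would remove the error. Whichever is used, the text should make clear that it refers to the acute-or-late rate.

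The cost is a wording change to one statement. N stays at 53, and the visits and the section 9.4.2 analyses stay as they are. The only downside is that the stated precision becomes less favourable.

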9.2.2 Accrual estimates

A total of 53 patients with very high-risk prostate cancer or with pelvic nodal involvement without distant metastases will be enrolled. Study accrual is anticipated to be approximately 3 patients per month, with a goal complete accrual by 24 months.

9.3 Interim Analyses and Stopping Rules

Continuous safety monitoring will be performed throughout the trial. The trial will be terminated if there is a greater 12% acute grade 3 toxicity. This rate is acceptable as prior studies have demonstrated 8-15% acute grade 3 GU and GI toxicity when irradiating the pelvis using standard fractionated technique to 45 Gy in 1.8 Gy fractions followed by brachytherapy boost

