3.4 Criteria for Termination of Protocol

The trial will be terminated if there is a greater than 12% clinically significant, treatment-Phase II – Enzalutamide and Radiation

related grade 3 or higher toxicity. The 12% clinically significant, treatment-related acute grade 3 or higher toxicity rate is acceptable as prior studies have demonstrated a 12% acute grade 3 GU and GI toxicity. The use of a urinary catheter or bladder irrigation within 14 days after brachytherapy will not be considered grade 2 toxicity as this may be a standard procedure after brachytherapy. The trial will not be terminated for non-related or non-clinically significant toxicities.

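### The toxicity stopping rule in 9.3 and 3.4 triggers at the 12% rate the plan calls acceptable, with no allowance for chance: at a true 12% it fires in 45-84% of trials, depending on how it is read

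*Combined protocol and SAP*

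**What the plan says.** - Section 9.3: "Continuous safety monitoring will be performed throughout the trial", and "The trial will be terminated if there is a greater 12% acute grade 3 toxicity". The justification follows: "This rate is acceptable as prior studies have demonstrated 8-15% acute grade 3 GU and GI toxicity".
- Section 3.4: "The trial will be terminated if there is a greater than 12% clinically significant", the event there being treatment-related toxicity of grade 3 or higher. It continues "The 12% clinically significant, treatment-related acute grade 3 or higher toxicity rate is acceptable"; the benchmark it gives is a 12% GU and GI rate seen in earlier studies. Its last sentence rules out termination for toxicities that are unrelated or not clinically significant.
- Section 9.2.1 takes about 12% as the usual rate, but for acute and late toxicity together: "If the true grade 3 or greater acute or late toxicity rate is 12%, with 47 patients".
- Section 2.4.1 ends the acute period at "90 days within the completion of radiotherapy". Section 7.1 makes every patient evaluable for toxicity from first study-drug treatment.
- Several review intervals appear: weekly Site Committee and six-weekly DSMC review of serious events (7.6), and monthly Site Committee and six-monthly data monitoring of 20% of subjects (Appendix 2). None is tied to the rule.

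**The concern.** A limit equal to the tolerated rate leaves no room for chance. If the true rate is 12%, the observed proportion will be above 12% about half the time at any one look, and repeated looks raise the chance that it is above at least once. The effect is strongest early: one event among the first eight assessed patients is at least 12.5% and meets the condition.

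Two results depend on this. Safety and PSA complete response are both primary objectives, and the sample size assumes about 47 evaluable patients. Following the rule could end the trial at a toxicity level the plan accepts before either is estimated as planned. Overriding it would depart from a sentence that says the trial will be terminated. The counted event is also worded differently in the two sections, so the same data could satisfy one and not the other.

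**Working it through.** **The plan's own figure.** No stopping probability is stated, so there is none to reproduce. The sample size does reproduce. With 70% against 85%, one-sided 0.05 and 80% power, the arcsine formula gives n = ((1.645 + 0.842) / (2·asin√0.85 − 2·asin√0.70))² = 46.7, so 47. Then 47 / 0.9 = 52.2, so 53.

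**Inputs.** N = 53 and 3 patients per month (9.2.2); trigger above 12% (9.3, 3.4); true rates 12% (called acceptable) and 8% and 15% (ends of the range in 9.3).

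**What the trigger means in counts.** It fires at 1 event in up to 8 patients, 2 in up to 16, 3 in up to 24 and 4 in up to 33. At 53 it needs 7 (7/53 = 13.2%; 6/53 = 11.3%). The chance of at least one event in the first 8 is 1 − 0.88⁸ = 64% at a true 12% and 1 − 0.92⁸ = 49% at a true 8%.

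**Denominator of fully assessed patients.** Exact binomial recursion over (patients, events), absorbing when events/n exceeds 0.12 at a look:

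| Looks | True 12% | True 8% | True 15% |
|---|---|---|---|
| Every patient | 84% | 62% | 93% |
| Every 3, plus final (monthly) | 81% | 58% | 92% |
| Six-weekly (4.5 patients: 5, 9, 14, 18 ... 50, 53) | 79% | 55% | 91% |
| Every 10, plus final | 69% | 38% | 85% |
| Six-monthly (18, 36, 53) | 60% | 26% | 79% |
| 27 and 53 | 55% | 21% | 76% |
| 25 and 50 | 49% | 18% | 71% |
| Once, at 53: P(X ≥ 7) | 45% | 13% | 70% |

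**Denominator of patients enrolled to date.** This is close to the treated-to-date reading that 7.1 suggests. It is a simulation at 3 patients per month, checked at each event. Event timing is assumed, because the documents give none:

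| Events become known | True 12% | True 8% | True 15% | Stopped before 53 enrolled, true 12% |
|---|---|---|---|---|
| Spread over months 0-6 | 65% | 35% | 82% | 59% |
| Spread over months 2-6 | 55% | 23% | 77% | 44% |
| All at month 6 | 48% | 15% | 72% | 22% |
| All at month 9 | 46% | 13% | 70% | 5% |

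**Stopping while accrual is open, assessed-patient denominator.** The acute outcome is complete about 8 weeks + 5 weeks + 90 days = 26 weeks after androgen deprivation starts, or 6 × 3 = 18 further patients. An IMRT boost of 19 fractions (about 4 weeks) and the 14-week start allowance in 5.1 extend this to about 10 months, or 30 patients. Counting only looks where assessed patients plus the lag is below 53, at a true 12%:

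- looks from every 10 to every patient: 60-81% (lag 18), 50-76% (lag 30);
- six-monthly: 37% at either lag, since only the look at 18 qualifies;
- two looks: 35-41% (lag 18), 0% (lag 30, as 25 + 30 and 27 + 30 exceed 53).

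**The case against.** **The denominator.** A reader might infer that the documents are silent on the denominator, and so take 69-84% as the rule's property. Section 7.1 does not allow that. It makes patients evaluable from first treatment, which points to a treated-to-date denominator and to about 46-65% at a true 12%. It is not written into the rule, however, and a patient counted from first dose has not completed the acute window, so the question stays open. The frequent-look figures are one conditional reading, and looks every 10 patients are an assumption, not a schedule in the plan.

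**Attribution.** A reader might infer that 9.3 and 3.4 conflict outright on attribution, since 9.3 names none. The last sentence of 3.4 largely settles this by excluding unrelated and non-clinically significant events from termination. What remains is grade 3 against grade 3 or higher, whether late events count (the stopping sentence in 3.4 omits the word acute), and whether the event is limited to GU and GI toxicity, as the benchmark is.

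**Acute window.** The wording in 9.4.2 about acute toxicity within 24 months concerns the final analysis. It is a separate point and does not change this rule.

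**The true rate.** The 12% and 8-15% are prior GU and GI rates. The counted event is filtered by relatedness but not limited to those organ systems, so its true rate could be higher or lower. The combined acute-or-late 12% in 9.2.1 is only indirect support. The probabilities are conditional on a true rate and do not predict this trial.

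**Strictness.** A hard ceiling for an untested combination is a defensible preference, and DSMC oversight adds judgment. Neither supplies the rule's error rates, and the text says termination will occur.

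**Conclusion.** The concern holds on every reading examined. At the rate the plan accepts, the rule fires in 45-84% of trials; at a true 8% in 13-62%; at a true 15%, the top of the range cited to justify the trigger, in 70-93%. The most lenient reading, a single look at 53, still fires in 45% at a true 12%, stops no accrual, and fits poorly with continuous monitoring.

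A reader might infer that an acceptable regimen would more likely than not be stopped during accrual. The documents do not support that as a general statement. At a true 12% the chance is about 5-59% with the enrolled denominator, 50-81% with frequent looks at assessed patients after the lag, 37% with six-monthly looks and 0-41% with two looks.

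These figures assume independent patients, a constant true rate, comparison of the observed proportion with 12%, and 53 patients assessed or enrolled at 3 per month. The enrolled-denominator figures also rest on the assumed event timing.

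**What to change.** 1. Reconcile the counted event in 3.4 and 9.3: grade 3 or grade 3 and higher, acute only or also late, GU and GI only or all. Carry the exclusion in 3.4 into 9.3. State the denominator, reconciled with 7.1, and the look schedule.
2. Replace the raw percentage with a tabulated sequential boundary that has a minimum number of patients and stated stopping probabilities over a range of true rates, for example 8-30%. How much excess to tolerate is for the sponsor and the DSMC.

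As an illustration of the trade-off only, take a Beta(0.12, 0.88) prior, looks at every assessed patient from patient 5, and stopping when the posterior probability that the rate exceeds 12% passes a cut-off:

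| Cut-off | True 8% | 12% | 15% | 20% | 25% | 30% |
|---|---|---|---|---|---|---|
| 0.97 | 2% | 10% | 24% | 56% | 82% | 95% |
| 0.90 | 10% | 28% | 48% | 78% | 94% | 99% |
| 0.80 | 18% | 44% | 65% | 88% | 97% | over 99% |

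The change costs protocol wording and one table, with no extra patients or data. The real downside is weaker protection against a modest excess: at a true 15% these boundaries stop 24-65% of trials, against 70-93% for the raw rule. At the final look they would let 11, 9 and 8 events in 53 pass (20.8%, 17.0%, 15.1%). If a strict ceiling is preferred, it should be chosen with figures of this kind stated.
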